13.4.3 Definition of adverse events of special interest (AESI)

An adverse event of special interest (AESI) is one of scientific and medical interest specific to understanding of durvalumab and may require close monitoring. An AESI may be serious or non-serious. If the Investigator has any questions regarding an event being an immune-mediated AE (imAE), the investigator should promptly contact the Chief Investigator.

AESIs observed with durvalumab include:

- Diarrhea / Colitis and intestinal perforation
- Pneumonitis / ILD
- Hepatitis / transaminase increases
- Endocrinopathies (i.e. events of hypophysitis/hypopituitarism, adrenal insufficiency, hyper- and hypothyroidism and type I diabetes mellitus)
- Rash / Dermatitis
- Nephritis / Blood creatinine increases
- Pancreatitis / serum lipase and amylase increases
- Myocarditis
- Myositis / Polymyositis
- Neuropathy / neuromuscular toxicity (e.g. Guillain-Barré, and myasthenia gravis)
- Intestinal Perforations

Other inflammatory responses that are rare/less frequent with a potential immune-mediated etiology include, but are not limited to:

- Pericarditis
- Sarcoidosis
- Uveitis
- Other events involving the eye and skin
- Hematological events
- Rheumatological events
- Vasculitis
- Non-infectious meningitis
- Non-infectious encephalitis

It is possible that events with an inflammatory or immune mediated mechanism could occur in nearly all organs.

In addition, infusion-related reactions and hypersensitivity/anaphylactic reactions with a different underlying pharmacological etiology are also considered AESIs.

Further information on these risks (e.g. presenting symptoms) can be found in the current version of the durvalumab Investigator's Brochure. More specific guidelines for their evaluation and treatment are

described in detail in the Dosing Modification and Toxicity Management Guidelines (please see Appendix 1). These guidelines have been prepared by the Sponsor to assist the Investigator in the exercise of his/her clinical judgment in treating these types of toxicities. These guidelines apply to AEs considered causally related to the study drug/study regimen by the reporting investigator.

13.4.4 Pneumonitis/ILD investigation

The following assessments, and additional assessments if required, will be performed to enhance the investigation and diagnosis of potential cases of pneumonitis.

- Physical examination: Signs and symptoms (cough, shortness of breath and pyrexia, etc.) including auscultation for lung field will be assessed.
- SpO2Saturation of peripheral oxygen (SpO2)
- When pneumonitis/ILD is suspected during study treatment, the following markers should be measured where possible: ILD Markers (KL-6, SP-D) and β-D-glucan
- Tumor markers: Particular tumor markers which are related to disease progression.
- Additional Clinical chemistry: CRP, LDH

13.5 Assessment of safety parameters

13.5.1 Assessment of severity

Assessment of severity is one of the responsibilities of the investigator in the evaluation of AEs and SAEs. Severity will be graded according to the NCI CTCAE v5.0. The determination of severity for all other events not listed in the CTCAE should be made by the investigator based upon medical judgment and the severity categories of Grade 1 to 5 as defined below.

Grade 1 (mild)	An event that is usually transient and may require only minimal treatment
Grade i imilai	an avant that is listially transfer and may reguling any minimal treatment
Grade I tillia	All Cyclic triat is assaily transicint and may reduite only infilling treatment

or therapeutic intervention. The event does not generally interfere with

usual activities of daily living.

Grade 2 (moderate)

An event that is usually alleviated with additional specific therapeutic

intervention. The event interferes with usual activities of daily living, causing discomfort but poses no significant or permanent risk of harm to

the patient.

Grade 3 (severe) An event that requires intensive therapeutic intervention. The event

interrupts usual activities of daily living, or significantly affects the clinical

status of the patient.

Grade 4 (life-threatening)

An event, and/or its immediate sequelae, that is associated with an

imminent risk of death or with physical or mental disabilities that affect or limit the ability of the patient to perform activities of daily living (eating,

ambulation, toileting, etc.).

Grade 5 (fatal) Death (loss of life) as a result of an event.

It is important to distinguish between serious criteria and severity of an AE. Severity is a measure of intensity whereas seriousness is defined by the criteria in Section 13.4.1. A Grade 3 AE need not necessarily be considered an SAE. For example, a Grade 3 headache that persists for several hours may not meet the regulatory definition of an SAE and would be considered a nonserious event, whereas a Grade 2 seizure resulting in a hospital admission would be considered an SAE.

13.6 Recording of adverse events and serious adverse events

AEs and SAEs will be collected from the time of the patient signing the ICF until the follow-up period is completed or 90 days after the last dose of study treatment. If an event that starts later is considered to be a late onset toxicity to study treatment, it should still be reported as an AE or SAE.

During study participation, all AEs and SAEs should be proactively followed up for each patient for

as long as the event is ongoing. Every effort should be made to obtain a resolution for all events, even if the events continue after the patient has discontinued study treatment or the study has completed.

Any AEs that are unresolved at the patient's last visit in the study are followed up by the Investigator for as long as medically indicated, but without further recording in the CRF.

AstraZeneca retains the right to request additional information for any patient with ongoing AE(s)/SAE(s) at the end of the study, if judged necessary.

The following variables will be collected for each AE:

- Type of event/description of AE
- Maximum CTCAE grade

In addition, the following variables will be collected for SAEs as applicable:

- Description of SAE
- Date the AE met criterion for SAE
- Seriousness criteria fulfilled
- Date of hospitalization
- Date of discharge
- The date when the AE started and stopped
- The maximum CTCAE grade reported
- Investigator causality rating against the study treatment or procedure, or concomitant medication
- Action taken with regard to study treatment
- Administration of treatment for the AE
- Outcome
- Probable cause of death
- Date of death
- Whether an autopsy was performed

The grading scales found in the NCI CTCAE version 5.0 will be utilized for all events with an assigned CTCAE grading. For those events without assigned CTCAE grades, the recommendation in the CTCAE criteria that converts mild, moderate, and severe events into CTCAE grades should be used. A copy of the CTCAE version 5.0 can be downloaded from the Cancer Therapy Evaluation Program website (http://ctep.cancer.gov).

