Blood for biomarker analyses		Х			X					
Stool for biomarker analyses°		X			X					

Study Number TRIPLEX
Protocol Version Number 1.1
Date 05-JAN-2022

Year Week	49	3	23	36	49	4	23	36	49	5	23	36	52	Progressive disease or patient lost to follow-up
Clinical examination/	.,	.,	.,	· ·	.,	.,	.,	.,	.,	V	.,	.,		.,
performance status/weight	X	X	X	X	X	X	X	X	X	X	X	X	X	X
HRQoL (QLQ C30 + LC13)	Х													X
Cognitive function (MoCA)					Х				Х				Х	X
Clinical chemistry ^e	X													X
Hematology ^f	X													X
Assessment of adverse events	Х	Х	Х	Х	Х	Х	Х	Х	Х	Х	Х	Х	Х	X
CT thorax/upper abdomen ^k	Х	Х	Х	Х	Х	Х	Х	Х	Х	Х	Х	Х	Х	X
MRI of the brain ^{k,m}	(X)°	Х	(X)°	Х	(X)°	Х	(X)°	Х	(X)°	X	(X)°	Х	(X)°	X
Blood for biomarker analyses	Х				Х				Х					X
Stool for biomarker analyses ^o	Х				Х				Х					X
Biopsy of progressing lesion ^o														X

Follow-up for patients who have completed study treatment: According to the study schedule.

Follow-up of patients who have discontinued study treatment due to other reasons than RECIST 1.1 progressive disease (PD) and need for other treatment: Should be followed according to the study schedule until RECIST 1.1 PD and need for other treatment.

Assessments at RECIST 1.1 PD: All evaluations and assessments listed in the last column of the study schedule ("PD") should be performed when disease progression occurs. If any assessment has been performed within the last 7 days, they do not need to be repeated, but it is essential that all assessments are performed (stool sampling and re-biopsy are not mandatory).

Follow-up for patients beyond RECIST 1.1 PD: As long as patients are considered to benefit clinically from continuing study treatment and are not in need for other systemic treatment, they can continue study treatment. This usually applies for patients who have completed chemoimmunotherapy and receive durvalumab monotherapy. A confirmatory CT evaluation should be performed within 4-6 weeks to ensure that they do not experience rapid disease progression requiring other therapy. At a minimum, subsequent intervals between CT evaluations should be according to the study schedule.

Follow-up for patients who discontinue study treatment due to RECIST 1.1 PD: Post-study AEs/SAEs should be reported according to protocol. Post-study treatment and survival must be recorded. Patients will be followed and treated according to local routines.

Table of contents	Page				
1. PROTOCOL SYNOPSIS	3				

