13.4.2 Definition of serious adverse events (SAEs)

An SAE is an AE occurring during any study phase (i.e., screening, run-in, treatment, wash-out, follow-up), at any dose of the study drugs that fulfils one or more of the following criteria:

- Results in death
- Is immediately life-threatening
- Requires in-patient hospitalization or prolongation of existing hospitalization
- Results in persistent or significant disability or incapacity
- Is a congenital abnormality or birth defect in offspring of the patient
- Is an important medical event that may jeopardize the patient or may require medical intervention to prevent one of the outcomes listed above.

Medical or scientific judgment should be exercised in deciding whether expedited reporting is appropriate in this situation. Examples of medically important events are intensive treatment in an emergency room or

at home for allergic bronchospasm, blood dyscrasias, or convulsions that do not result in hospitalizations, or development of drug dependency or drug abuse.

The causality of SAEs (their relationship to all study treatment/procedures) will be assessed by the investigator(s) and immediately reported to the central trial office on the SAE form (i.e. no more than 24 hours after learning of the event) by emailing the completed SAE-form to [contact].

Exception An event that leads to hospitalization under the following circumstances should not be reported as an adverse event or a serious adverse event:

- Hospitalization for respite care
- Planned hospitalization required by the protocol (e.g., for study treatment administration or performance of an efficacy measurement for the study) or to perform study procedures
- Hospitalization for pre-existing conditions, provided that the hospitalization was planned prior to the study and the patient has not experienced an adverse event
- Hospitalization due solely to progression or suspicion of progression of the underlying cancer

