13.6.1 Study recording period and follow-up for adverse events and serious adverse events

If a patient discontinues from treatment for reasons other than disease progression, and therefore continues to have tumor assessments, SAEs related to study treatment of procedures must be captured until the patient is considered to have confirmed PD and will have no further tumor assessments. The investigator is responsible for following all SAEs until resolution, until the patient returns to baseline status, or until the condition has stabilized with the expectation that it will remain chronic, even if this extends beyond study participation.

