13.12 Deaths

All deaths that occur during the study treatment period, or within the protocol-defined follow-up period after the administration of the last dose of study drug, must be reported as follows:

- Death clearly resulting from disease progression should be reported to the Study Monitor/Physician at the next monitoring visit and should be recorded in the CRF. It should not be reported as an SAE.
- Where death is not due (or not clearly due) to progression of the disease under study, the AE
 causing the death must be reported to the Study Monitor/Physician as an SAE within 24 hours. It
 should also be recorded in the CRF.
- The report should contain a comment regarding the co-involvement of PD, if appropriate, and should assign main and contributory causes of death.
- Deaths with an unknown cause should always be reported as an SAE. It should also be recorded in the CRE
- A post-mortem may be helpful in the assessment of the cause of death, and if performed, a copy of the post-mortem results should be forwarded to the central trial office in Trondheim.

Deaths occurring after the protocol defined safety follow-up period after the administration of the last dose of study drug should be recorded in the CRF. If the death occurred as a result of an event that started after

the defined safety follow-up period and the event is considered to be due to a late onset toxicity to study drug, then it should also be reported as an SAE.

13.13 Reporting of serious adverse events and serious unexpected adverse reactions to the IRB and/or the Regulatory Authority

All SAEs must be reported, whether or not considered causally related to the investigational product. The Sponsor is responsible for informing the IRB and/or the Regulatory Authority of SAEs and SUSARs as per local requirements.

If any SAE occurs, investigators or other site personnel must inform appropriate Sponsor within one day i.e., immediately but no later than 24 hours of when he or she becomes aware of it.

For fatal or life-threatening adverse events where important or relevant information is missing, active follow-up is undertaken immediately. Investigators or other site personnel inform Sponsor representatives of any follow-up information on a previously reported SAE within one calendar day i.e., immediately but no later than 24 hours of when he or she becomes aware of it.

The reference document for definition of expectedness/listedness is the IB for durvalumab.

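### The end of adverse event collection is stated inconsistently, and under two of the rules a late event enters only if an unblinded investigator attributes it to study treatment

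*Protocol*

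**What the plan says.** Frequency and severity of adverse events is a secondary endpoint (protocol section 14.1). Section 14.3.1 compares it between arms by chi-square or Fisher's exact test. The trial is open label (section 9.1.1), and section 4.4 treats the question whether TRT adds side effects as essential to the trial.

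The period of collection is described in several places:

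- Section 13.6 runs collection from consent "until the follow-up period is completed or 90 days after the last dose of study treatment". It adds: "If an event that starts later is considered to be a late onset toxicity to study treatment, it should still be reported as an AE". The same rule covers serious events.
- Section 13.6.1 deals with patients who stop treatment for reasons other than progression: "SAEs related to study treatment of procedures must be captured until the patient is considered to have confirmed PD".
- The notes to the schedule (section 2) say of the same patients: "Should be followed according to the study schedule until RECIST 1.1 PD and need for other treatment". The schedule marks AE assessment at its visits through year 5. For patients who stop because of progression, the notes say only: "Post-study AEs/SAEs should be reported according to protocol".
- Section 13.4.2: "An SAE is an AE occurring during any study phase (i.e., screening, run-in, treatment, wash-out, follow-up").
- Section 13.13: "All SAEs must be reported, whether or not considered causally related to the investigational product".
- Section 13.12 has a separate rule that begins "Deaths occurring after the protocol defined safety follow-up period". No period is defined under that name.

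**The concern.** There are two linked problems.

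First, a site cannot tell from the text when to stop recording. Two sites could each comply and still deliver different AE data.

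Second, where collection of all events ends early, later events pass through an attribution filter. The investigator who applies it knows the arm. In the experimental arm a late pulmonary, oesophageal or cardiac event has one more candidate cause than in the control arm, namely TRT; section 8.3.7 lists lungs, oesophagus and heart as organs at risk. The same event could then be recorded in one arm and left out in the other, and the toxicity comparison would partly measure attribution. This differs from unequal observation time, because it can occur when both arms are observed equally long.

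**Working it through.** The protocol states no figure on this point, so there is none to reproduce. The check is a comparison of the rules, followed by two illustrative calculations.

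**1. The rules side by side**

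| Place | Events | End | Relatedness required? |
|---|---|---|---|
| 13.6 | AEs and SAEs | End of follow-up or 90 days after last dose, neither given priority | Not before the end; yes after it |
| 13.6.1 (off treatment, no progression) | SAEs | Confirmed progression | Yes |
| Schedule (same patients) | AEs | Progression and need for other treatment | No |
| 13.4.2 and 13.13 | SAEs | Any phase, including follow-up | No |
| 13.12 | Deaths | A safety follow-up period not defined under that name | Yes, for SAE reporting of a death from an event starting after it |

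For an SAE in a patient off treatment without progression, 13.6.1 names related events only, while 13.13 requires all. For a non-serious AE in the same patient more than 90 days after the last dose, the schedule assesses it, 13.6 may or may not admit it, and 13.6.1 does not mention it.

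**2. How far apart the two readings of 13.6 are**

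Follow-up lasts at most 5 years, that is 5 × 52 = 260 weeks. The 90-day reading ends at (week of last dose) + 90/7.

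- Last dose at course 4, week 9: 9 + 12.9 = week 21.9; gap 260 − 21.9 = 238.1 weeks.
- Last dose at week 52: week 64.9; gap 195.1 weeks.
- Last dose at week 104: week 116.9; gap 143.1 weeks.

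If TRT is complete by week 6 (assumed), the first of these windows closes 21.9 − 6 = 15.9 weeks after TRT.

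**3. Could the analysis repair it?**

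For each AE, 13.6 lists only the type of event and the maximum grade. Start and stop dates and the causality rating are listed only for SAEs. On those variables, non-serious AEs cannot be cut back to a common window afterwards, nor can late attributed events be separated out.

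**4. What unequal attribution could do (illustration)**

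Inputs: n = 302/2 = 151 per arm (section 14.4, 1:1). Assumed: the same true late-event rate r in both arms; attribution probability a, by arm; late events independent of earlier ones. The in-window rate b is zero (late events tested alone), 10% (assumed, for a specific event), or 62%, the grade 3-4 rate that section 4.5.2 gives for the earlier durvalumab trial.

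Recorded rate in an arm: p = b + (1 − b) × r × a.

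Example with b = 0.62, r = 0.10: TRT 0.62 + 0.38 × 0.10 × 0.50 = 0.639; control 0.62 + 0.38 × 0.10 × 0.10 = 0.6238.

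Test: z = (pT − pC) / √(2p̄(1 − p̄)/n). A false TRT excess is z > 1.96, with probability summed over the two binomial distributions. The nominal value in that direction is 2.5%.

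| In-window rate b | Attribution, TRT vs control | r = 10% | r = 20% |
|---|---|---|---|
| None (late only) | 50% vs 10% | 53.9% | 87.1% |
| None (late only) | 50% vs 30% | 13.4% | 24.2% |
| None (late only) | 50% vs 40% | 5.9% | 8.6% |
| 10% | 50% vs 10% | 15.2% | 41.1% |
| 10% | 50% vs 30% | 6.5% | 12.9% |
| 62% | 50% vs 10% | 4.6% | 7.9% |
| 62% | 50% vs 30% | 3.4% | 4.6% |

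With Fisher's exact test, the two figures in the first row fall to about 40% and 81%.

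**The case against.** The strongest reply is that the bias depends on the reading. If the end of follow-up governs 13.6, all events are collected without a filter for as long as the patient is followed, and the imbalance largely disappears. This is correct. The conflict and the bias are therefore not cumulative: the bias arises only under the 90-day reading or under 13.6.1. But the text does not choose the harmless reading.

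It can also be said that 13.6.1 sets a minimum for one group of patients, and that a grid of visits is not a stop rule. That softens the conflict but does not remove it. A minimum limited to related SAEs is still at odds with 13.13, and nothing tells a site what to do with AEs found at scheduled visits after the 90 days.

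A reader might infer that late events will be counted in the TRT arm and missed in the control arm. The documents do not support that. The wording of 13.6 is the same for both arms, and control patients also receive study treatment. Section 13.4.3 lists pneumonitis and myocarditis among the events of special interest with durvalumab, and pericarditis among rarer, possibly immune-mediated responses, so late lung and heart events have a candidate cause in both arms. TRT is an extra cause, not the only one. While durvalumab continues, including beyond progression, the window also stays open in both arms.

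Finally, how AE tables separate periods is commonly left to a statistical analysis plan, which is not at hand. That stands: the silence of 14.3.1 on this is not itself a fault. What is collected, and whether it carries a date, is fixed by the protocol.

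**Conclusion.** The point holds as an inconsistency in the current text with a possible bias as its consequence. Sections 13.6, 13.6.1, 13.12, 13.13 and the schedule do not give one end of AE/SAE collection, and the two readings of 13.6 can differ by 143 to 238 weeks in the examples above. Under the 90-day reading, or under 13.6.1, late thoracic events may be recorded more readily in the experimental arm.

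The size of that bias cannot be derived from the documents. The attribution rates, the late-event rates and the independence of late from earlier events are all assumed. With 50% versus 10% attribution and a 10% late-event rate, the chance of a false TRT excess is about 5% when late events are added to a 62% in-window rate, and 54% when they are tested alone. It is tempting to read the larger figure as the expected error of the safety comparison. It is not: it needs both an extreme attribution contrast and a test confined to late events, and milder contrasts bring it close to nominal. The change should be made because it is cheap and because the listed variables would not allow a later repair.

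**What to change.** - Reconcile 13.6, 13.6.1, 13.12, 13.13 and the schedule to one end of AE/SAE collection, identical in both arms, with all events recorded within it regardless of attribution. If two dates are kept, say whether the earlier or the later governs, and use one named period throughout, including for deaths.
- Add an onset date to the variables recorded for every AE, since 13.6 now lists dates only for SAEs.
- In 14.3.1, base the between-arm comparison on all-cause AEs with onset in that window. Continue to report later attributed events for safety, listed by arm and kept out of the tested counts.

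The cost is wording plus one field in the case report form, using visits already scheduled. The small downside is that toxicity arising after the window is described rather than tested, which should be weighed when the length of the window is chosen.

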1. PROTOCOL SYNOPSIS

Study title: Randomized phase III trial investigating the survival benefit of adding thoracic radiotherapy (TRT) to durvalumab immunotherapy plus chemotherapy in extensive stage small-cell lung cancer

Protocol version number: 1.0

Clinical phase: Randomized phase III

Study duration: From 2021 until 2028

Investigational therapies and reference therapy:

- Reference therapy: Durvalumab plus carboplatin/etoposide
- Investigational therapy: Durvalumab plus carboplatin/etoposide and TRT

Research hypotheses:

The main hypothesis is that adding TRT to durvalumab plus chemotherapy provides a survival benefit for patients with extensive stage (ES) small-cell lung cancer (SCLC).

Specifically, we hypothesize that:

- combining TRT, durvalumab and chemotherapy is feasible and well tolerated
- adding TRT improves survival, response rates, and PFS
- the patients who benefit the most from the study treatment can be identified through analyses of tissue, blood and stool samples
- toxicity of prophylactic cranial irradiation (PCI) is acceptable in ES SCLC patients who receive durvalumab plus chemotherapy

Objectives:

Primary Objective:

To investigate whether adding TRT to durvalumab plus chemotherapy improves 1-year survival.

Secondary Objectives:

To investigate whether adding TRT improves 2-, 3-, 4- and 5-year overall survival.

To investigate whether adding TRT improves overall response rates, response rates in non-irradiated lesions and PFS.

To investigate whether TRT improves local control.

To compare the frequency and severity of adverse events between the treatment arms.

To compare health related quality of life between treatment arms.

Exploratory Objectives:

To compare the duration of severe adverse events between the treatment arms.

To compare the frequency and timing of brain metastases between treatment arms.

To assess cognitive function in the whole study cohort and compare cognitive function between those who receive PCI and those who do not.

To investigate associations between outcomes of study treatment and biomarkers in tissue, blood and stool (e.g. ctDNA in blood, miRNA, gut microbiome).

Endpoints:

Primary Endpoint:

1-year overall survival

Secondary Endpoints:

2-year, 3-year, 4-year and 5-year overall survival

Overall response rates

Response rates in non-irradiated lesions

Progression free survival

Progression free survival in non-irradiated lesions

Local control rates in the thorax

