Frequency and severity of adverse events

Health-related quality of life

Exploratory Endpoints:

Duration of severe adverse events

Frequency and timing of brain metastases

Cognitive function in patients who receive PCI and those who do not

Associations between outcomes of study treatment and biomarkers in tissue, blood and stool (e.g. ctDNA in blood, miRNA and gut microbiome).

Study population:

Patients with ES SCLC eligible for chemo-immunotherapy and TRT.

[figure not shown]
Number of centers: Approx. 25

Number of patients: Approx. 302

Study design:

Open label randomized phase III trial

Figure 1 Study design

Randomization:

Patients will be randomized 1:1 in blocks of various sizes to receive chemo-immunotherapy alone or chemo-immunotherapy plus TRT stratifying for presence of liver metastases (yes vs. no) and presence of brain metastases (yes vs. no).

Inclusion criteria:

1. Capable of giving signed informed consent which includes compliance with the requirements and restrictions listed in the informed consent form (ICF) and in this protocol. Written informed consent

and any locally required authorization (e.g. Health Insurance Portability and Accountability Act in the US, European Union [EU] Data Privacy Directive in the EU) obtained from the patient/legal representative prior to performing any protocol-related procedures, including screening evaluations.

- 2. Age \geq 18 years at time of study entry.
- 3. ECOG performance status of 0 or 1.
- 4. Body weight >30 kg.
- 5. Adequate normal organ and marrow function as defined below:
 - Haemoglobin ≥10.0 g/dL.
 - Absolute neutrophil count (ANC) ≥1.5 × 10⁹ /L
 - Platelet count ≥100 × 10⁹/L
 - Serum bilirubin ≤1.5 x institutional upper limit of normal (ULN). This does not apply to patients with confirmed Gilbert's syndrome (persistent or recurrent hyperbilirubinemia that is predominantly unconjugated in the absence of hemolysis or hepatic pathology).
 - ALT (SGPT) \leq 2.5 x institutional upper limit of normal unless liver metastases are present, in which case it must be \leq 5 x ULN.
 - Measured creatinine clearance (CL) >40 mL/min or Calculated creatinine CL>40 mL/min by the Cockcroft-Gault formula (Cockcroft and Gault 1976) or by 24-hour urine collection for determination of creatinine clearance.
- 6. Patient is willing and able to comply with the protocol for the duration of the study including undergoing treatment and scheduled visits and examinations including follow-up.

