13.8 Adverse events based on signs and symptoms

All AEs spontaneously reported by the patient or reported in response to the open question from the study personnel: "Have you had any health problems since the previous visit/you were last asked?" or revealed by observation will be collected and recorded in the CRF.

When collecting AEs, the recording of diagnoses is preferred, when possible, to recording a list of signs and symptoms. However, if a diagnosis is known and there are other signs or symptoms that are not generally part of the diagnosis, the diagnosis and each sign or symptom will be recorded separately.

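### Start and stop dates are required only for SAEs, so the exploratory endpoint on duration of severe adverse events cannot be computed for severe events that are not serious

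*Protocol*

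**What the plan says.** Among the exploratory objectives in the Protocol synopsis (section 1) is "To compare the duration of severe adverse events between the treatment arms". The matching exploratory endpoint, in the synopsis and again in section 14.1, is "Duration of severe adverse events".

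Section 13.6 sets out what is recorded, in two lists. The first is introduced by "The following variables will be collected for each AE" and has two entries: the type or description of the event, and "Maximum CTCAE grade". The second list is additional and applies to SAEs only. Among its entries is "The date when the AE started and stopped".

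Section 13.5.1 labels Grade 3 as severe and asks the investigator to keep severity and seriousness apart. It says "A Grade 3 AE need not necessarily be considered an SAE", and gives as an example that "a Grade 3 headache that persists for several hours may not meet the regulatory definition of an SAE".

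**The concern.** A duration needs an onset and an end. For an AE that is not an SAE, the variables listed in section 13.6 supply neither. The endpoint is worded in terms of severity, while the dates are tied to seriousness, and the protocol itself says that these differ.

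With only the required variables, the comparison between arms would cover the severe events that also met a seriousness criterion. That is a different set of events from the one the endpoint names. An analysis plan can define how duration is measured, but it cannot supply dates that the protocol did not require sites to record. For this reason the point belongs to the protocol and cannot simply be left to the analysis plan.

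**Working it through.** The protocol states no figure to reproduce and no calculation applies. The check sets what the endpoint needs against what is required to be collected.

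1. **What the endpoint needs.** For each severe AE: its grade, to establish that it is severe; a start date; and a stop date.

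2. **What is required for every AE (section 13.6, first list).** Description and maximum CTCAE grade. The grade is there. Neither date is.

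3. **What is required in addition for SAEs (section 13.6, second list).** One entry gives the start and stop of the event. The other dates in that list (seriousness criterion met, hospitalization, discharge, death) do not define the duration of the event.

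4. **Whether severe AEs that are not SAEs exist under the protocol.** They do. Section 13.5.1 says so and gives the Grade 3 headache as an example.

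5. **Which events fall into the gap.** Severe is read here as Grade 3 or higher. Section 13.5.1, for events without a CTCAE entry, describes Grade 4 as life-threatening and Grade 5 as fatal, which largely overlaps the seriousness criteria in section 13.4.2. Under section 13.9, a non-serious deterioration in a protocol-mandated laboratory value is not reported as an AE unless it leads to discontinuation of study treatment. What remains is mainly clinical, non-serious Grade 3 events.

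6. **Whether another section requires the missing dates.** None does. Section 13.6 asks for follow-up while an event is ongoing, but follow-up is not a recorded date. Section 13.8 has patients asked "Have you had any health problems since the previous visit/you were last asked", which elicits events and does not require dates. Section 17 has staff enter into the CRF the data that the protocol requires, and these dates are not among them.

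From the required variables, then, duration is computable for SAEs and not computable for severe AEs that are not SAEs.

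**The case against.** The strongest reply is that the list in section 13.6 may not be exhaustive. The CRF and the study procedure manual are separate and not shown. Some of the protocol's own rules presuppose knowledge of timing: section 13.4.1 distinguishes treatment-emergent from other AEs, and section 13.6 sets a 90-day window after the last dose and provides for late-onset toxicity. The dates may therefore be collected in practice. This stands as a limit on the conclusion: loss of data is not established. It does not remove the mismatch, because the protocol does not require the dates that its own endpoint needs.

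A second reply is that severe was meant as serious. If so, the endpoint is computable, but the wording is then wrong in the synopsis and in section 14.1, since section 13.5.1 separates the two terms. Either reading calls for a correction.

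A reader might also infer three stronger points that the documents do not support.

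- **Bounds on duration from the visit schedule.** The protocol nowhere proposes to derive duration from visits. AE assessments are not evenly spaced, and durvalumab every 4 weeks brings patients in between the 8-weekly assessments that start at week 21. Any such bound would depend on which visits were chosen.
- **That the SAE dates are also inadequate because they do not give time spent at Grade 3 or higher.** The endpoint reads naturally as the duration of events graded severe. Choosing between whole-event duration and time at grade is a definition that the analysis plan may make.
- **That the laboratory rules distort the AE comparison.** Section 13.4.1 tells sites to report certain abnormal laboratory findings as AEs, while section 13.9 limits this for protocol-mandated values. Section 13.9 is the more specific rule and gives its reason: the values are already in the CRF. What is missing is a cross-reference, and no effect on results is shown.

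**Conclusion.** The concern holds for one exploratory endpoint. As section 13.6 is written, the duration of severe AEs can be computed only for those that are also SAEs, so the endpoint as named cannot be delivered from the required variables.

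The size cannot be given as a number, because the protocol does not say what share of severe AEs is expected to be non-serious. The conclusion rests on two assumptions: that severe means Grade 3 or higher, and that the CRF collects what section 13.6 lists and no more. If the CRF already holds start and stop dates for these events, the fault is confined to the protocol text.

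The primary endpoint does not depend on these dates. Nor does the secondary comparison of AE frequency and severity, which needs only the event and its grade. The point still deserves action, because the correction is cheap and dates that are not recorded at the time may be hard to recover.

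**What to change.** First check whether the CRF already records start and stop dates for AEs that are not SAEs. Then do one of the following:

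- **If severe is meant:** add start and stop dates to the variables in section 13.6 for every AE of Grade 3 or higher. The cost is two date fields, a short amendment and a little extra data entry at sites. If the CRF already has the fields, only the protocol text changes.
- **If serious is meant:** reword the exploratory objective and endpoint in the synopsis and the endpoint in section 14.1. This needs no new data, but the comparison then no longer covers severe events that are not serious.

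In the same amendment, one sentence in section 13.4.1 pointing to the exception in section 13.9 would reconcile the laboratory wording. This is a minor edit.
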